## 4. Hypothesis and Objectives

Taking all into account, the present project will try to evaluate the role of the combination of encorafenib and binimetinib administered before local treatment that will follow, after response.

## 4.1. Study Hypothesis

The main hypothesis is that:

 Intracranial response rate by modified RECIST 1.1 before local treatment will be ≥40% in cohort 1 and 2.

Study will be considered positive if the main hypothesis is achieved.

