# 10. STATISTICS

# 10.1. Sample size calculation

# Sample size calculation:

The sample calculation has been done for the **initially proposed primary endpoint (cohort 1)** and it's based on a Fleming's Single Stage Procedure:

We want to show that the Intracranial response rate by modified RECIST 1.1 before local treatment is superior or equal to the reference value, say, 90=40%. Under the hypothesis to have a response rate under new treatment ( $\pi$ 1) of 60% with  $\alpha$  risk = 5% in one-sided test and a power of 80%, the required sample size is 38 patients.

Finally, assuming that, 20% of patients will be lost of follow up, die or progress before day 56 without doing the first tumour assessment (according data published in COMBI-MB study), the initial sample size will be 48 patients, to obtain 38 evaluable patients.

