# 10.2. Study endpoints

Intracranial objective response (iORR) rate by modified RECIST 1.1 before local treatment in cohort 1 and 2: iORR calculated as the proportion of patient with a best overall intracranial response of complete response (CR) or partial response (PR) before local treatment in cohort 1 and 2. The final statistical analysis of this endpoint is expected to be performed within 3 months after the local treatment of the last patient in any cohort. iORR will be also reported separately for both cohorts.

**Duration of intracranial response in both cohorts (iDOR):** Calculated as the time from the date of first documented CR or PR to the first documented intracranial progression or death due to underlying cancer, in patients with documented intracranial CR or PR before local treatment. The final statistical analysis of this endpoint is expected to be performed within 6 months after database closure expected at 24 months after last patient inclusion, however interim analysis might be performed when analysing other primary variables.

The intracranial progression free survival (iPFS) by modified RECIST in both cohorts: iPFS is defined as the time from the date of inclusion to the date of the first documented intracranial disease progression or death due to any cause, whichever occurs first. PFS will be determined based on tumour assessment (modified RECIST version 1.1 criteria). The local Investigator's assessments will be used for analyses. Those patients who are alive and have not progressed at the last follow-up, date of progression will be censored at the date of the last follow-up. Patient with no additional image test other than baseline will be censored to the day after to inclusion. The final statistical analysis of this endpoint is expected to be performed within 6 months after database closure expected at 24 months after last patient inclusion, however interim analysis might be performed when analysing other primary variables.

Percentage of patients free of intracranial progression at 6 (week 24), 12 (week 48) and 24 months (week 96) in both cohorts: percentage of patients free of intracranial progression assessed by modified RECIST at 6 months (week 24), 12 months (week 48) and 24-month (week 96) considering date of inclusion. The final statistical analysis of this endpoint is expected to be

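### Section 4.1 calls the study positive at a response rate of 40% or more, but 40% is the rate the design is meant to exclude; on the observed rate, a true 40% would pass about 46% of the time

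*Combined protocol and SAP*

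**What the plan says.** Protocol section 4.1 states the main hypothesis as "Intracranial response rate by modified RECIST 1.1 before local treatment will be ≥40% in cohort 1 and 2" and adds: "Study will be considered positive if the main hypothesis is achieved". It does not say whether this refers to the observed rate, a confidence limit or a test.

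Section 10.1 and the synopsis say the aim is to show that the rate "is superior or equal to the reference value" of 40%. On the sample size, 10.1 says "it's based on a Fleming's Single Stage Procedure", with a 60% alternative and "risk = 5% in one-sided test and a power of 80%, the required sample size is 38 patients". Allowing for 20% without a first assessment, "the initial sample size will be 48 patients, to obtain 38 evaluable patients". Section 10.1 attaches this calculation to cohort 1, as the primary endpoint proposed at the outset.

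The current primary endpoint covers cohorts 1 and 2 (synopsis objectives, 3.0.1, 4.2, 10.2); 10.2 adds "iORR will be also reported separately for both cohorts". Only the synopsis statistics paragraph still calls cohort 1 primary and cohort 2 exploratory.

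Section 10.6 promises exact 95% confidence intervals for proportions. SAP section 3.1 uses both ITT and PP for the main efficacy analysis without ranking them. The tables in SAP sections 4.1 and 4.2 show response at 56 days with no reference rate, test or threshold.

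**The concern.** In a superiority test against 40%, a rate equal to 40% is the null hypothesis and cannot count as success. Section 4.1 nevertheless puts the bar there. The test that would protect the conclusion appears only in the sample-size text, for an endpoint that has since been widened.

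The trial has no control arm, so the comparison with 40% is its whole confirmatory claim. Protocol section 3 reports 39% for dabrafenib alone in patients without previous local treatment, so 40% is close to what single-agent therapy gave. A rule that passes at 40% would not separate the combination from that benchmark.

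**Working it through.** **Inputs.** p0 = 0.40, p1 = 0.60, one-sided α = 0.05, power 0.80, 20% loss (10.1); cohorts of 48 and 15, total 63 (synopsis). The documents plan no pooled evaluable N. Assuming 20% loss in cohort 2 as well, it is 38 + 12 = 50; cohort 2 losses of 40% to 0% give 47 to 53.

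**The plan's own figures.** n = [(1.645·√(0.4·0.6) + 0.842·√(0.6·0.4)) / 0.20]² = 37.1, rounded up to 38. Then 38/0.80 = 47.5, rounded up to 48. Both reproduce.

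**Rule in 4.1 applied to the observed rate.** The pass probability is P(X ≥ r) for X ~ Binomial(N, p), with r the smallest count giving r/N ≥ 0.40.

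| N | r | Pass at true 40% | Pass at true 35% |
|---|---|---|---|
| 38 (cohort 1 evaluable) | 16 | 45.6% | 22.5% |
| 48 (cohort 1 ITT) | 20 | 46.1% | 20.6% |
| 50 (pooled evaluable, assumed) | 20 | 55.4% | 27.4% |
| 63 (pooled ITT) | 26 | 46.6% | 18.0% |

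Over N = 47 to 53 the pass probability at a true 40% runs from 46.1% to 55.4%. If each cohort had to reach 40% separately, it is 0.461 × 0.597 = 27.5% (48 and 15) or 0.456 × 0.562 = 25.6% (38 and 12).

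**The design's test.** The exact cut-off c is the smallest count with P(X ≥ c | 0.40) ≤ 0.05. Fleming's formula, N·p0 + 1.645·√(N·p0·q0), gives 20.17, 24.78, 25.70 and 31.60. The nearest integer plus one is 21, 26, 27 and 33, the same as the exact cut-offs.

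| Cut-off | α | Power at 60% | One-sided 95% lower bound | Two-sided 95% lower limit |
|---|---|---|---|---|
| 21/38 (55.3%) | 4.1% | 77.8% | 40.7% | 38.3% |
| 26/48 (54.2%) | 3.3% | 83.5% | 41.4% | 39.2% |
| 27/50 (54.0%) | 3.1% | 84.4% | 41.5% | 39.3% |
| 33/63 (52.4%) | 3.1% | 91.3% | 41.3% | 39.4% |

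**Where the two rules disagree.** Counts of 16–20/38, 20–25/48, 20–26/50 and 26–32/63 pass 4.1 on the observed rate but fail the test. At N = 38 the one-sided p-values for 16 to 21 responders are 0.456, 0.330, 0.222, 0.138, 0.078 and 0.041.

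**Effect of not naming the population.** If the 20% without an assessment count as non-responders in ITT, 21/38 in PP (p = 0.041) becomes 21/48 = 43.8% (p = 0.35). Pooled, 27/50 (p = 0.031) becomes 27/63 = 42.9% (p = 0.37). Under the same convention the true ITT rate is 0.60 × 0.80 = 0.48, and power is 23.9% at 26/48 and 28.4% at 33/63.

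**The case against.** Section 4.1 is headed as a hypothesis. A hypothesis normally concerns the true rate and is judged by the planned test. Sections 4.1 and 10.1 share the endpoint wording and the 40%, so a reader could take the one-sided 5% test as the intended route to success, and the inclusive wording as loose drafting. The exact 95% interval in 10.6 would also show readers that 40% is not excluded at the disputed counts. The SAP consists largely of table shells, so the absence of a test there is weak evidence.

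The Fleming reading is possible, and the 46% is therefore the error of the observed-rate reading only. But the Fleming reading does not complete the plan: the test was set for cohort 1 alone, and no count, cohort set or population is fixed for the present endpoint. A descriptive interval is not a decision rule. At the test's own cut-offs the two-sided interval still includes 40%, so it would not give the same verdict either.

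The ITT figures depend on counting non-evaluable patients as non-responders, which the documents do not state; the SAP tables keep them as a separate row. Choosing between ITT and PP is secondary to the missing rule.

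**Conclusion.** The concern holds. As written, 4.1 sets the success threshold at the null rate, and nothing else in the protocol or SAP states that 40% must be rejected for the cohorts 1 and 2 endpoint. Conditional on the observed-rate reading, the false-positive probability at a true 40% is about 46% at the planned sizes (46.1% to 55.4% for a pooled evaluable N of 47 to 53, which rests on an assumed cohort 2 loss), against a stated 5%. Requiring each cohort to pass still leaves about 26% to 28%. On the Fleming reading the error rate is controlled, but the outcome can turn on a set nobody has named. The binomial figures assume independent patients with a common response rate.

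**What to change.** Replace the wording in protocol 4.1, 10.1 and the synopsis with: H0: rate ≤40%; H1: rate >40%; the study is positive only if the exact one-sided binomial p against 40% is ≤0.05 in the deciding set.

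- Name one deciding set identically in the synopsis, 4.1, 10.1 and SAP 3.1 and 4. For cohorts: 1 and 2 pooled, as in 3.0.1 and 10.2 (correcting the synopsis statistics paragraph), or cohort 1 if the sponsor keeps the endpoint that was sized. For population: evaluable/PP, the basis of the sizing, or ITT. Report the other sets as secondary.
- Print the cut-off for the actual N, with the one-sided 95% exact lower bound (the lower end of a two-sided 90% interval) beside the result.
- State in 10.6 that the two-sided exact 95% interval is descriptive and can include 40% when the test is positive.
- If ITT decides, state how non-evaluable patients count and the resulting power.
- SAP section 3.5 already refers to database closure. If the rule is fixed after that point, say so in the report.

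The cost is wording, one p-value and one bound; no patients or data are added. The observed bar rises from 40% to about 52%–55%, and exact power at 38 is 77.8%, not 80% (80% is first reached at n = 42). Using the two-sided 95% interval as the rule instead would need 22/38, 27/48, 28/50 or 34/63 and cut power to 67.0%, 75.3%, 76.6% or 86.5%. PP leaves out patients who die or progress before day 56 without a scan; ITT includes them but loses most of the power under the plan's 20% assumption if they count as non-responders.

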## 4.2. Study Objectives

## 1. Primary objective:

a. Intracranial objective response rate by modified RECIST 1.1 before local treatment in cohort 1 and in cohort 2.

#### 2. Secondary objectives:

[figure not shown]
- a. Intracranial objective response rate assessed by the investigators using modified RECIST 1.1 before local treatment in cohort 2.
- b. Intracranial objective response rate assessed by the investigators using modified RECIST 1.1 before local treatment in cohort 1.
- c. The duration of the intracranial response in both cohorts assessed by the investigators using modified RECIST 1.1.
- d. The intracranial progression free survival by modified RECIST in both cohorts
- e. Percentage of patients free of intracranial progression according to modified RECIST at 6 (week 24), 12 (week 48) and 24 months (week 96) in both cohorts.
- f. Percentage of patients free of extracraneal progression according to RECIST 1.1 () at 6 (week 24), 12 (week 48) and 24 months (week 96) in both cohorts.
- g. Overall survival in both cohorts.
- h. Percentage of alive patients at 6, 12 and 24 months in both cohorts.
- i. Toxicity of the combination until local treatment in both cohorts:
  - Toxicity of the combination after local treatment in both cohorts.
  - Quality of life in both cohorts.

## 5. STUDY DESIGN

[figure not shown]
## 5.1. Overall Study Design

This is a phase II clinical trial with two cohorts of patients, all with melanoma BRAF mutant and brain metastases:

 Cohort 1: patients with asymptomatic brain metastases and without previous radiotherapy (previous surgery is allowed) treatment in the brain. N=48

• Cohort 2: patients with symptomatic brain metastasis and without previous radiotherapy (previous surgery is allowed)treatment in the brain. N=15

The design includes local confirmation of BRAF mutation, screening phase, systemic treatment phase, radiotherapy or radiosurgery (according to the radiotherapist criteria, following the indications included in the protocol), and guality of life assessment.

#### 5.2. Patient Screening

Once completed all regulatory and Sponsor requirements and after received the "Open To Enrolment Letter" (OTEL), confirming that study is fully active in the corresponding site, the trial (informed consent) can be offered to potential patients.

Informed consent will be obtained prior to start of the specified screening window. Procedures conducted as part of the subject's routine clinical management (e.g., blood count determinations and imaging studies such as bone scans) prior to signing of informed consent may be used for screening or for defining baseline data, provided these procedures are conducted as specified in the protocol. Once informed consent form (ICFs) is signed, a trial screening number will be assigned to each patient after registering at Electronic Data Capture (EDC) platform. Each site will receive access to the EDC platform to register each screened case, since as per GCP guidelines it is mandatory to register every patient who signs a consent form.

Furthermore, within the Investigator Site File (ISF), a Patient Identification List will be included in order to identify patients according to local normal practice. This document will allow for immediate and unequivocal identification of patients participating in this clinical trial. This document will always be stored under Investigator staff custody at the site. The screening number will identify patients throughout the screening period while procedures needed to confirm the subjects' suitability for the trial protocol, such as clinical laboratory tests, imaging, and others are performed.

Screening determinations include obtaining informed consent, signature and registration, patient record review, local BRAF mutation status, clinical consultation, imaging procedures, and laboratory analyses including haematology, biochemistry, and urine tests. Additional information about screening procedures can be found in section 8 of this protocol.

## 5.3. Patient Inclusion and Cohort Assignment

During the screening (28 days before day 1 cycle 1) it should be assessed whether the patient is symptomatic (cohort 2) or asymptomatic (cohort 1).

Definition of Asymptomatic (cohort 1):.Patients without active symptoms secondary to brain metastases at the moment of inclusion.

After confirming that a patient fulfils all eligibility criteria of the study (inclusion/exclusion criteria), site staff will initiate the eCRF registration procedure.

Once procedure is fulfilled the site staff will receive the "Inclusion confirmation communication", and protocol-specific treatment can be initiated.

This is an open label, single arm study including two cohorts of patients, in each cohort, patients will be treated with encorafenib 450 mg once daily and binimetinib 45 mg twice daily.

After 56 days of treatment, a contrast enhanced brain MRI and CT body scan will be performed as first tumour assessment:

- Patients with PD at first evaluation in brain MRI (modified RECIST 1.1 criteria) and /or body CT scan (RECIST 1.1 criteria) will discontinue study treatment and will continue in the study for OS follow-up.
- Patients with CR in brain (modified RECIST 1.1) and no PD in the body (RECIST 1.1), will continue study treatment and will be followed every two months with contrast enhanced brain MRI and body CT scan up to 12 months. If no PD after one year, patients will be followed as per institutional criteria, and continue with the treatment.
  - o If considered by the investigator, local treatment can be done for brain CR patients, but only after confirming no safety concerns (defined as substantial deterioration of vital signs (including ECOG PS), physical examination, ECG, Lab. Values that do not recommend RT) with the three first patients treated with radiation therapy in the running phase (for more information, please see section 9.1).
- Patients with no CR and no PD in brain MRI per modified RECIST 1.1 criteria, and no PD in body per RECIST 1.1 criteria, will be treated with local RT and/or radiosurgery, and then will continue Enco and Bini. The first 3 patients will be treated in a running

phase. These three first patients, that have achieved non-CR, non-PD in brain and no PD in body, are going to be treated sequentially or at the same time depending on when radiotherapy treatment is needed. If no safety concerns appear (defined as substantial deterioration of vital signs (including ECOG PS), physical examination, ECG, Lab. Values that do not recommend RT), the rest of patients that have achieved non-CR, non-PD in brain will begin local treatment when it will be indicated under medical criteria:

- Encorafenib and binimetinib will be interrupted 24h before radiotherapy and restart 24h after the last dose of radiotherapy.
- The local radiation technique will be defined and indicated by the radiotherapy oncologist (local co-investigator) criteria, depending on the number of lesions and its maximum size in the last tumour assessment done during the treatment with encorafenib and binimetinib:
  - \*Radiosurgery (RS) or Stereotactic radiosurgery (SRS):
    - 1 brain metastases < 4 cm
    - ≤ 3 brain metastases ≤ 3 cm
    - ≤ 4 brain metastases ≤ 2.5 cm

\*Radiosurgery: for patients who do not meet criteria for radiosurgery (RS) or (SRS), exceptional cases could be allowed after prior detailed consultation with the trial coordinators.

- Whole brain radiotherapy (WBRT):
  - ≥ 4 brain metastases
  - Almost one brain metastasis of ≥ 4 cm
  - ≤ 4 brain metastases not eligible for RS or SRS

Location metastases: brain stem, midbrain, pons, medulla or within 10 mm of the optic nerves and chiasm.

- After the first evaluation of the patient's intracranial response, patients without progression who received a local treatment, could receive other local treatments at the discretion of the investigator, if this is considered beneficial for the patient.
- Surgery can be done if, as per investigator criteria, is necessary for the patient's health.
- For patients in CR in the first assessment, if they were not treated with radiation, and in follow up a PD occurs **only in the brain**, brain local treatment will be carried out as per protocol. These patients can continue encorafenib and binimetinib treatment after local treatment.
- Every patient with a stable disease or response in both, brain and body, in the first assessment, when presenting a DP after local treatment in the body CT scan by RECIST 1.1. and/or brain MRI, by modified RECIST 1.1, they will discontinue the systemic treatment with encorafenib and binimetinib.

- After progression, patients will be followed only for overall survival.
  - o In case of encorafenib and binimetinib are providing a clinical benefit to any patient, treatment could be continued after discussion with Sponsor if it agrees on that. In this case, follow up will be done as per institutional criteria. In the study, these patients will be followed only for overall survival.
- Study assessments: in each monthly visit, adverse events will be registered, blood samples will be collected for blood cell counts and general biochemistry (including magnesium, potassium and creatinine-kinases); an ECG will be performed at baseline, after one month of treatment, and every 3 months thereafter; a left ventricular ejection fraction (LVEF) evaluation will be performed by as per institutional guidelines at baseline and every 3 months thereafter ophthalmologic anamnesis and evaluation will be performed by oncologist at baseline and in every monthly visit, if there's any alarm symptom or sign, patient will be evaluated by Ophthalmologist. Body CT-scan and contrast enhanced brain MRI will be performed baseline and every 8 weeks up to 12 months and according to normal practise thereafter. More information regarding study determination is provided in section 8 of this protocol.

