- 11. Patients relapsing to a prior adjuvant therapy (e.g. IFN, IL-2 therapy, any other immunotherapy, radiotherapy or chemotherapy) are allowed. When patients received BRAF +/- MEK inhibitors as adjuvant treatment, relapse must have occurred ≥ 12 months after the end of it. Moreover, patient mustn't present any residual grade 3-4 toxicity, including medically serious and reversible/controlled toxicities (e.g.: GGT elevation, CPK elevation, vomiting)

- 12. Steroids or anticonvulsants are allowed if clinically needed and once the patient is included in the trial are not being administered in an increasing dose.
- 13. Female subjects must either be of non-reproductive potential (e.g., post-menopausal by history: ≥60 years old and no menses for ≥1 year without an alternative medical cause; OR history of hysterectomy, OR history of bilateral tubal ligation, OR history of bilateral oophorectomy) or must have a negative urine pregnancy test upon study entry. If the result in the urine pregnancy test is positive, a serum pregnancy test should be done to confirm pregnancy.
- 14. Normal functioning of daily living activities.
- 15. Willingness and ability to attend scheduled visits, follow the treatment schedule and undergo clinical tests and other study procedures.

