## 7. OTHER ANALYSES REQUIRED BY THE COORDINATOR

Group A: Symptomatic patients (Those belonging tp symptomatic cohort 2).

Group B: Asymptomatic patients, both those who were not treated with corticosteroids or anticonvulsants and those who were treated without association with brain metastases.

Group C: Patients who were asymptomatic at the time of study treatment but had been treated with corticosteroids in the days before due to a symptom of the disease.

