## 7.3. PRIMARY EFFICACY OBJECTIVE: RESPONSE AT 56 DAYS

Table 165: Symptomatic group (A+C): intracranial Objective Response Rate at 56 days

ORR: Intracraneal Evaluation at 56 days	N	%	95%CI
CR or PR			
SD			
NE			
Total			

Table 166: Asymptomatic group (B): intracranial Objective Response Rate at 56 days

ORR: Intracraneal Evaluation at 56 days	N	%	95%CI
CR or PR			
SD			
Total			

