#### 3. COHORTS A-C (SYMPTOMATIC PATIENTS)

Analyses were conducted exclusively on significant variables across the entire sample.

3.1.1.GLOBAL HEALTH STATUS/QoL

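### The SAP analyses recently steroid-treated but symptom-free patients (group C) as symptomatic; for quality of life this split replaces the protocol cohorts, leaving cohort 1 without a result

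*Combined protocol and SAP*

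**What the plan says.** **Cohort definition.** Protocol 5.3 defines the asymptomatic cohort as "Patients without active symptoms secondary to brain metastases at the moment of inclusion". The sentence before it gives the timing of the assessment: "During the screening (28 days before day 1 cycle 1) it should be assessed whether the patient is symptomatic". Inclusion criterion 12 in section 6.1 adds that "Steroids or anticonvulsants are allowed if clinically needed", provided the dose is not rising once the patient is in the trial. It does not distinguish between cohorts, so steroid use does not in itself move a patient out of cohort 1.

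**SAP grouping.** SAP section 7, whose title says the analyses were requested by the coordinator, defines three groups:
- A: "Symptomatic patients (Those belonging tp symptomatic cohort 2".
- B: asymptomatic patients without corticosteroids or anticonvulsants, plus "those who were treated without association with brain metastases".
- C, described as "Patients who were asymptomatic at the time of study treatment but had been treated with corticosteroids in the days before due to a symptom".

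**Where it is used.** A and C together are called symptomatic, and B alone asymptomatic. The split is applied to OS (SAP 7.1), iPFS (7.2) and day-56 response (7.3, under a heading that names the primary efficacy objective; Table 165 is titled "Symptomatic group (A+C): intracranial Objective Response Rate at 56 days"). The addendum, which is the second set of tables, uses it for baseline data, radiotherapy and ePFS. The QoL report, the third set, heads its section 3 "COHORTS A-C (SYMPTOMATIC PATIENTS") and its section 4 as cohort B. No table title or legible column heading gives group C on its own.

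**What is kept.** SAP section 4 tabulates response, OS, iPFS and ePFS for all patients and for protocol cohorts 1 and 2.

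**The concern.** The words symptomatic and asymptomatic carry two meanings in one set of results. Under the protocol, group C sits on the asymptomatic side; in SAP 7, the addendum and the QoL report it sits on the symptomatic side. Two things are at stake.

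The first is a secondary objective. Protocol 4.2 lists quality of life in both cohorts. If QoL is split only by the relabelled groups, that objective is not answered for the larger cohort.

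The second is interpretation elsewhere. Moving a group of patients from one column to another changes both columns without any change in a patient's outcome. A reader who takes A+C and B for the protocol cohorts would attribute that change to the disease or the treatment.

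**Working it through.** **1. Where group C belongs.** The protocol has two cohorts. The SAP sets group A equal to cohort 2. If the three groups do not overlap, C lies outside cohort 2 and is therefore part of cohort 1. The SAP's own description of C as asymptomatic agrees with this.

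**2. Which results exist by protocol cohort.**

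| Result | Cohort 1 | Cohort 2 | A+C and B |
|---|---|---|---|
| Day-56 response | SAP 4.1, 4.2 | SAP 4.1, 4.2 | SAP 7.3 |
| OS | SAP 4.5 | SAP 4.5 | SAP 7.1 |
| iPFS | SAP 4.6 | SAP 4.6 | SAP 7.2 |
| ePFS | SAP 4.7 | SAP 4.7 | Addendum 2.4 |
| QoL | none | SAP 4.8 | QoL report 3 and 4 |

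SAP 4.8 is headed cohort 2. QoL report section 2 gives one undivided set of 16 scale tables for all patients. Sections 3 and 4 give 4 tables each, for A with C and for B. The only empty cell is cohort 1 QoL.

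**3. Cohort sizes used below.** These come from protocol 10.1 and the synopsis, and the planned figure reproduces. With null rate 0.40, target 0.60, one-sided 5% and 80% power,

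n = [(1.645·√0.24 + 0.842·√0.24) / 0.20]² = 37.1, rounded up to 38; 38/0.8 = 47.5, rounded up to 48.

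Cohort 2 has 15 patients, for a total of 63. The relabelling does not touch this calculation.

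**4. Effect of the labels on a response rate.** Write a, b, c for the rates in A, B, C and m for the size of C.

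- Protocol cohort 1 = [(48 − m)·b + m·c]/48. The SAP's asymptomatic group = b, which is higher if and only if b > c.
- Protocol cohort 2 = a. The SAP's symptomatic group = (15·a + m·c)/(15 + m), which is higher if and only if c > a.
- Both rise if and only if a < c < b. The pooled rate over all 63 is the same either way.

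The documents give neither m nor any of the three rates for this trial, so every row below is an assumption, with m = 10. The 58% and 59% are the asymptomatic (no previous local therapy) and symptomatic rates that protocol section 3 cites from the dabrafenib–trametinib brain-metastasis trial.

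| a, b, c (%) | Cohort 1 → B | Cohort 2 → A+C | Pooled |
|---|---|---|---|
| 40, 65, 50 | 61.9 → 65.0 | 40.0 → 44.0 | 56.7 |
| 50, 60, 55 | 59.0 → 60.0 | 50.0 → 52.0 | 56.8 |
| 59, 58, 58.5 | 58.1 → 58.0 | 59.0 → 58.8 | 58.3 |
| 59, 58, 40 | 54.2 → 58.0 | 59.0 → 51.4 | 55.4 |
| 59, 58, 70 | 60.5 → 58.0 | 59.0 → 63.4 | 60.1 |
| 65, 55, 60 | 56.0 → 55.0 | 65.0 → 63.0 | 58.2 |

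First row in full: (38·0.65 + 10·0.50)/48 = 29.7/48 = 61.9%; (15·0.40 + 10·0.50)/25 = 11/25 = 44.0%.

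Varying m over 5, 10, 15 and 20 in that row, cohort 1 is 63.4, 61.9, 60.3 and 58.8 against B at 65.0. Cohort 2 at 40.0 becomes 42.5, 44.0, 45.0 and 45.7.

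**The case against.** The best defence is that the A/B/C analyses are additions. They sit in a section marked as requested by the coordinator, the groups are defined at its start, and most titles carry A+C or B. The primary endpoint is response in both cohorts together, which no relabelling can alter. No hypothesis compares the cohorts, and cohort 2 is described as exploratory. Grouping recently symptomatic patients with symptomatic ones is a reasonable exploratory question. All of this stands for response, OS, iPFS and ePFS, where the protocol-cohort tables are kept. It does not stand for QoL, where the relabelled split is the only one that includes most of cohort 1.

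It can also be said that group C is recoverable by subtracting B from cohort 1. That works for counts only if both tables use the same population, which the SAP 7 tables do not name, and only if B and C make up all of cohort 1. A symptom-free patient given only anticonvulsants because of brain metastases fits neither group. Kaplan-Meier medians cannot be subtracted. A cohort 1 QoL mean could be back-calculated from the all-patient and cohort 2 tables if population and data lock agree, but medians, ranges and the Wilcoxon comparisons could not.

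Three stronger readings are tempting and are not supported:
- *The split inflates both groups.* This requires group C's outcome to lie above A's and below B's. The documents give no size or outcome for C, and the response rates they cite produce almost no shift.
- *The grouping was chosen after the results were seen.* The trial is open label and the QoL report says its subgroup analyses were restricted to variables significant in the whole sample, but the documents do not date the request for the grouping.
- *Section 5.3 contradicts itself by naming both screening and inclusion.* The first sentence says when status is assessed and the next says what the status means. The two are compatible.

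**Conclusion.** The point holds as a reporting gap with a limited reach. Group C belongs to cohort 1 by the protocol's definition and is analysed as symptomatic in SAP 7, the addendum and the QoL report. The firm consequence is that no table reports QoL for protocol cohort 1, although a secondary objective asks for it.

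For the other endpoints the consequence is a risk of misreading. With 10 patients in C, the assumed response rates above move a by-symptom figure by between 0.1 and 7.6 points (59.0 to 51.4), upwards or downwards. With the cited 58% and 59% and C between them, the movement is negligible. These sizes rest on assumed rates and an assumed size of C. The pooled primary result and the sample size are unaffected. The change should be made, but it does not threaten the trial's main conclusion.

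**What to change.** - Add QoL tables for protocol cohort 1 and cohort 2, with the same scales and time points as the all-patient tables.
- In SAP 7, the addendum and the QoL report, show A, B and C in separate columns with their numbers, alongside protocol cohorts 1 and 2, and state that C is part of cohort 1.
- Label any A+C versus B contrast, including the tables in SAP 7.3 under the primary efficacy heading, as post hoc and exploratory. Do not present it as the protocol's symptomatic and asymptomatic result, and do not call these groups cohorts.
- So that the three columns add up to the whole sample, state the time window meant for prior corticosteroids in group C and where patients treated only with anticonvulsants for brain metastases are counted.

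The screening sentence in protocol 5.3 needs no change. The cost is extra columns and one set of QoL tables from data already collected. The drawback is that the group C column may hold few patients, so its figures will be imprecise.
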